1.1 Primary Objective

The primary objective of this study is to monitor the safety profile of Trajenta in Korean patients with type 2 diabetes mellitus (T2DM) in a routine clinical setting.

1.2 Secondary Objective

The secondary objective of the study is to monitor the effectiveness of Trajenta by evaluating the change from baseline to endpoint in the glycosylated hemoglobin (HbA1c), fasting plasma glucose (FPG) of Korean T2DM patients.

2. Study Period and Study Method

2.1 Study Period

This rNIS is a prospective, non-interventional, open-label, multi-centre study. As per regulation, the re-examination period extends from 14 Sep 2011 until 13 Sep 2017 (6 years). However, active enrollment is to be initiated in 2012 after finalizing the re-imburement agreement with the authority. Before initiation of the study, any newly reported adverse events collected from other sources such as spontaneous cases, literature cases etc will be closely monitored. The last patient follow up is expected in 2016.

2.2 Number of Subjects

A total of 3,000 patients will be enrolled at approximately 80 sites by as many as 100 or more NIS physicians. To minimize the selection bias at the site level, the goal is to have participating centers reflect a balance between general hospitals and clinics for surveillance. The treating physicians will mainly be internists. To minimize the selection bias, consecutive patients from each site who meet inclusion criteria will be enrolled in this study.

	CONFIDENTIAL :	Last Update Date
	THIS DOCUMENT AND INFORMATION CONTAINED HEREIN IS PROPRIETARY TO COMPANY AND IS NOT TO BE DISCLOSED WITHOUT THE WRITTEN PERMISSION OF COMPANY.	21-AUG-2017
STATISTICAL ANALYSIS PLAN(V3.0)		

2.3 Study Population

2.3.1 Inclusion Criteria

- Patients who have been started on Trajenta in accordance with the approved label in Korea
- Patients who have signed on the data release consent form

2.3.2 Exclusion criteria

- Patients with previous exposure to Trajenta
- Current participation in clinical trials

2.4 Study Method

This is a prospective, non-interventional, open-label, multi-centre study. It will provide additional safety information of Trajenta in Korean patients with type 2 diabetes mellitus in routine clinical settings.

3. Analysis Sets

3.1 Safety Analysis Set

Subjects who administrated Trajenta at least once will be included in the safety analysis set.

Reflecting MFDS guideline, the subjects below shall be excluded from safety analysis set in the following order:

- (1) Subjects administered Trajenta prior to the contract date
- (2) Subjects who have not taken Trajenta
- (3) Follow-up failure: The subjects whose safety follow up have not been completed
- (4) Subjects who were prescribed for other indications except target indication:
 - [Target indication]
 - Patients with type 2 diabetes mellitus

	CONFIDENTIAL :	Last Update Date
	THIS DOCUMENT AND INFORMATION CONTAINED HEREIN IS PROPRIETARY TO COMPANY AND IS NOT TO BE DISCLOSED WITHOUT THE WRITTEN PERMISSION OF COMPANY.	21-AUG-2017
STATISTICAL ANALYSIS PLAN(V3.0)		

- (5) Subjects who violated inclusion/exclusion criteria
- (6) Subjects who did not follow dosage/capacity
 - [Dosage/Capacity]
 - The recommended dose 5 mg once daily
 - Administration by monotherapy
 - Combination with metformin
 - Combination with sulfonylurea
 - Combination with both sulfonylurea and metformin
 - Combination with insulin
 - Combination with both insulin and metformin
 - Combination with both empagliflozin (25mg) and metformin
- (7) Subjects of contraindications
 - Who are hypersensitive to the principle components and additives of this product
 - Patients with type 1 diabetes or diabetic ketoacidosis
- (8) Subjects who are not Korean

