3.2 DISCUSSION OF STUDY DESIGN

This is a single arm study with linagliptin.

Loss to follow up

All efforts will be made to minimize loss to follow up, particularly in the tracking of lost patients. To the extent possible, occurrence of adverse event, at minimum, for patients lost to follow up will be obtained. This allows assessing the impact of informative censoring due to treatment discontinuation. Also, patients lost to follow up will be characterized compared to the remaining patients and reason and time point of loss to follow up will be evaluated.

Channeling bias

Channeling bias can occur due to preferential prescribing in relation to different risks for the events of interest: e.g., if linagliptin would be more often prescribed to higher risk patients compared to other treatments, higher incidences of outcome events were then expected in the linagliptin group.

Confounding

As in any observational study, confounding may affect the estimation of associated between drug exposure and outcome of interest and statistical techniques. However, as only major confounders for selected research questions can be captured, residual (unmeasured) confounding may remain.

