7.3 PLANNED ANALYSES

7.3.1 Safety analyses

Demographic and baseline characteristics will be summarized descriptively for the entire cohort of eligible patients.

Adverse events (AEs) will be coded according to the latest version of Medical Dictionary for Drug Regulatory Affairs (MedDRA) coding system. Concomitant therapies will be coded according to the latest version of KIMS (Korea Index of Medical Specialties) coding system. The trial database will not be locked until coding is complete.

Safety analyses will be based on all patients treated, i.e. all patients who received at least one dose of Trajenta. However, if data for patients who have been treated with Trajenta beyond the scope of approved label are collected, separate safety analyses will be performed. Safety analyses will be performed based on demographics and baseline characteristics.

Patients lost to follow up will be characterized compared to the remaining patients and reason and time point of loss to follow up will be evaluated.

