6.3.2 Adverse Events by Preferred Terms

All AEs recorded in the CRF will be classified by body organs and terms under the classification standard of MedDRA terms, and all AEs excluding the AEs where causal relationship with Trajenta is “Unlikely” will be treated as AEs which causality cannot be excluded (hereafter “Adverse Drug Reaction(ADR)”).

For subjects to whom AE occurred, the incidence proportion of AEs and the number of AEs will be summarized.

Details are as follows.

- ① The frequency and percentage of the number of AEs according to serious adverse event, intensity, outcome of the event, action taken, causality, therapy of the event will be calculated.
- ② All AEs will be classified into the preferred terms according to serious adverse event, intensity, outcome of the event, action taken, causality, therapy of the event. The frequency and percentage of the number of each AE will also be calculated.
- ③ The number of subjects and the number of AE/ADR, Serious AE/Serious ADR, unexpected AE/ADR, unexpected Serious AE/unexpected Serious ADR will be calculated according to the preferred terms. In this case, the following subgroups are presented separately. Also, the incidence proportion and its 95% confidence interval will be estimated.
 - All of safety analysis set
 - Short-term effectiveness analysis set (Administration of Trajenta less than 24 weeks)
 - Long-term effectiveness analysis set (Administration of Trajenta for 24 weeks or more)
 - Subjects in effectiveness analysis set who administered DPP-4 inhibitor before administration of Trajenta
 - Subjects in effectiveness analysis set who did not administer DPP-4 inhibitor before administration of Trajenta
- ④ Preferred terms of Serious AE/Serious ADR, unexpected AE/ADR will be presented respectively according to the proportion of AE in the local product document.
- ⑤ For subjects excluded from the safety analysis set[†], the number of subjects and the number of AE/ADR, Serious AE/Serious ADR, unexpected AE/ADR, unexpected Serious AE/unexpected Serious ADR will be calculated according to the preferred terms. Also, the incidence proportion and its 95% confidence interval will be estimated.

[†]Subject excluded from safety analysis set: ‘Subjects who have not taken Trajenta’ and ‘Follow-up failure’ of patients excluded from safety analysis sets will be excluded (Reflecting the Ministry of Food and Drug Safety (MFDS) guideline).

	CONFIDENTIAL :	Last Update Date

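### The SAP leaves treated patients with incomplete safety follow-up out of both the safety set and the excluded-subject AE table, against the protocol's all-treated rule, and lists neither their number nor the promised lost-versus-remaining comparison

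*SAP*

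**What the plan says.** Safety is the primary objective (Protocol 2.2.1, SAP 1.1). Protocol 7.3.1 states: "Safety analyses will be based on all patients treated, i.e. all patients who received at least one dose of Trajenta". Protocol 5.1.1 uses the same at-least-one-dose population for the safety endpoint. The one exception in 7.3.1 is off-label use, which is analysed apart and not dropped: if data on patients "treated with Trajenta beyond the scope of approved label are collected, separate safety analyses will be performed".

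The protocol also plans for patients who are lost. Section 3.2 says that, as far as possible, "occurrence of adverse event, at minimum, for patients lost to follow up will be obtained", and gives the purpose: "This allows assessing the impact of informative censoring due to treatment discontinuation". Sections 3.2 and 7.3.1 both commit to a comparison, "Patients lost to follow up will be characterized compared to the remaining patients", and to an evaluation of why and when they were lost.

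SAP 3.1 opens with the same at-least-once rule. It then says that, reflecting the MFDS guideline, "the subjects below shall be excluded from safety analysis set in the following order". Never-treated subjects are item 2. Item 3 is "Follow-up failure: The subjects whose safety follow up have not been completed". SAP 6.3.2 item 5 plans an AE table for subjects outside the safety set, but its footnote says that the never-treated and the follow-up failures "of patients excluded from safety analysis sets will be excluded". SAP 7.4 repeats the footnote.

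**The concern.** Patients who stop attending may do so because of an adverse event. The protocol recognises this and asks for their AE data so that informative censoring can be examined. If the SAP then leaves those patients out of the incidence analysis and out of the side table, the reported incidence describes only patients whose safety follow-up was completed, and nothing in the planned output shows how different the others were. Without a count of follow-up failures, a reader of the final report cannot tell whether the omission is trivial or material.

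**Working it through.** **Tracing the text**

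1. The SAP exclusions run in order. Never-treated subjects leave at item 2, so item 3 removes treated patients. Protocol 7.3.1 would keep them.
2. The excluded-subject AE table (SAP 6.3.2 item 5) drops two categories by footnote: never treated and follow-up failure. The other six categories (1 and 4 to 8) stay in it. Follow-up failure is therefore the only treated category named as left out of both the safety-set incidence analyses and that table.
3. An off-label patient with incomplete follow-up is taken at item 3, before the indication and dosage exclusions. That patient also misses the SAP's nearest counterpart to the protocol's separate off-label analysis.
4. SAP 7.1 lists four totals: contracted, CRFs retrieved, safety set and effectiveness set. The number of follow-up failures cannot be derived from them.
5. SAP 7.2 to 7.4 list no lost-versus-remaining comparison and no time of loss. The reason for premature withdrawal (SAP 6.1, 6.3.1) is analysed only within the safety set, after these patients have left it.
6. The SAP gives no criterion for completed safety follow-up.

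**Illustration of size**

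The plan has no figure to reproduce. The 3,000 is a regulatory requirement (Protocol 7.6), and no loss rate, AE rate or observation time is given. Assume 3,000 treated, incidence p = 15% in retained patients, a lost fraction l, and a risk ratio r in lost against retained patients.

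True all-treated incidence = (1 − l)·p + l·p·r. The SAP set reports 15.0% throughout. Its 95% CI half-width is 1.96·√(0.15·0.85/n), with n = 3,000·(1 − l). The gap exceeds the half-width when r is above 1 + half-width/(l·p).

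| Lost | n kept | r = 0.5 | r = 1 | r = 2 | r = 3 | Half-width (points) | r needed |
|---|---|---|---|---|---|---|---|
| 2% | 2,940 | 14.9% | 15.0% | 15.3% | 15.6% | 1.29 | 5.30 |
| 5% | 2,850 | 14.6% | 15.0% | 15.8% | 16.5% | 1.31 | 2.75 |
| 10% | 2,700 | 14.3% | 15.0% | 16.5% | 18.0% | 1.35 | 1.90 |
| 20% | 2,400 | 13.5% | 15.0% | 18.0% | 21.0% | 1.43 | 1.48 |

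For ratios below 1, no value reaches the half-width at 2% or 5% lost. It takes r below about 0.10 at 10% and below about 0.52 at 20%.

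**Would a crude all-treated proportion recover the gap?**

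Assume a constant hazard, with lost patients observed for a fraction f of the 24 weeks. Their observed incidence is 1 − (1 − p·r)^f. At l = 0.10:

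- r = 1, f = 0.5: 0.9·0.15 + 0.1·(1 − 0.85^0.5) = 0.135 + 0.0078 = 14.3%, against a true 15.0%.
- r = 2, f = 0.5: 0.135 + 0.1·(1 − 0.70^0.5) = 0.135 + 0.0163 = 15.1%, against a true 16.5%.

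In the second case the crude figure recovers about 0.1 of the 1.5 points. In the first it is further from the truth than the SAP set.

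Now take first AEs over person-time to first AE or end of observation. Person-time per patient is (1 − e^(−h·f))/h with h = −ln(1 − p·r).

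- Retained patients: 0.15/0.923 = 16.25 per 100 person-24-weeks.
- All treated, r = 1: also 16.25, so there is no dilution.
- All treated, r = 2, f = 0.5: 0.1513/(0.9·0.923 + 0.1·0.458) = 0.1513/0.8765 = 17.3.
- Everyone fully observed, r = 2: 0.165/(0.9·0.923 + 0.1·0.841) = 0.165/0.9148 = 18.0.

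The rate recovers more than half of the difference (about 1.0 of 1.8), though not all of it.

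**The case against.** The strongest reply is that *follow-up failure* has a narrow meaning. The SAP analyses AE incidence by reason for premature withdrawal within the safety set, and it plans tables for patients with under 24 weeks of administration within its analysis sets. If failure meant not reaching the final visit, few premature withdrawals would be left to tabulate. A meaning such as no usable safety information after dosing fits better, and then few or no recorded AEs are lost. This is plausible but not conclusive: stopping the drug is not the same as being lost, and a patient who completes at 22 weeks also counts as short-term.

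Second, SAP 6.3.2 opens by classifying all AEs recorded in the CRF, and its items 1 and 2 name no population. AEs from follow-up failures may enter there. Those items give counts and percentages of events, not incidence, so they would not replace the missing analysis.

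Third, the SAP attributes the exclusion to the MFDS guideline, which is not among the documents. That may justify a restricted set, but it does not reconcile the SAP with Protocol 7.3.1.

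Fourth, the protocol's promised comparison still binds even if SAP section 7 does not repeat it, and sequential exclusions usually yield counts by reason. That lowers the weight of the omission but does not close it.

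A reader might also take Protocol 5.1.2.2 and 6.2.3 as rival definitions of completion. They are not: the first sets the window for collecting AEs, the second covers following up AEs already noted. The gap is only that the SAP states no criterion.

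**Conclusion.** The point stands as a conflict between protocol and SAP on the primary objective, together with an undefined term, an unlisted count and an unlisted comparison. Confidence in these is high, because they rest on the text alone.

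A reader might go further and infer that recorded AEs will be lost or that the reported incidence will be too low. The documents do not support that. The meaning of completed is open, no loss or AE rate is given, and lost patients could have lower, equal or higher risk. Reporting of individual SAEs to the sponsor is not affected by these analysis-set rules. Nor do the documents say whether the footnote also covers a follow-up failure already removed under category 1.

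Under the assumed 15% incidence, the effect is small at 2 to 5% lost unless lost patients differ strongly (a ratio above 5.30 or 2.75 to exceed the CI half-width). It becomes visible at 10% lost with about twice the risk (16.5% against 15.0%), and at 20% lost with about 1.5 times the risk. Which case applies cannot be known without the count that the SAP omits. It should be fixed.

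**What to change.** Keep the MFDS-restricted safety set as the regulatory presentation, and add the following.

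1. The AE, SAE and ADR analysis in all patients with at least one dose, as Protocol 7.3.1 states. Beside the crude proportion, give incidence per observed person-time, from first dose to last safety contact where recorded, because partly observed patients dilute the crude figure. AE onset is a planned item (Protocol 8.4.2). Total administration period (SAP 6.1) is treatment time and should not stand in for observation time.
2. Treated follow-up failures in the excluded-subject AE table, or in a separate listing, using whatever AE data were recorded.
3. The number of follow-up failures in SAP 7.1, and the protocol's lost-versus-remaining table with reason and time of loss.
4. In SAP 3.1, the criterion that makes safety follow-up completed.

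The cost is SAP wording and a few more tables. There will be two AE incidences to explain, and the all-treated one may be higher or lower. Stating the criterion may change who is in the restricted set.

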3.3.2 Inclusion criteria

- Patients who have been started on Trajenta in accordance with the approved label in Korea
- Patients who have signed on the data release consent form

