4.2 CONCOMITANT THERAPY, RESTRICTIONS, AND RESCUE TREATMENT

The protocol will allow additional drugs considered necessary for the patient's welfare to be prescribed at the discretion of the treating physician. It is required, however, to record the details of all concomitant medication administered to the patient during the course of treatment in eCRF. This includes concomitant therapies started one month prior to Trajenta initiation until the patient completes the final follow-up visit.

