5.1.2 Assessment of adverse events

5.1.2.1 Definitions of adverse events

Adverse event

An adverse event (AE) is defined as any untoward medical occurrence, including an exacerbation of a pre-existing condition, in a patient in a clinical investigation who received a pharmaceutical product. The event does not necessarily have to have a causal relationship with this treatment.

Serious adverse event

A serious adverse event (SAE) is defined as any AE which results in death, is immediately life-threatening, results in persistent or significant disability / incapacity, requires or prolongs patient hospitalisation, is a congenital anomaly / birth defect, or is to be deemed serious for any other reason if it is an important medical event when based upon appropriate medical judgement which may jeopardise the patient and may require medical or surgical intervention to prevent one of the other outcomes listed in the above definitions.

Adverse drug reaction

Adverse drug reaction (ADR) refers to any harmful, unintended reaction to the pharmaceutical product of any dose at which a causal relationship with the pharmaceutical product cannot be ruled out.

Non serious adverse drug reaction

Non serious adverse drug reaction is defined as any ADR which does not meet the SAE criteria.

Intensity of adverse event

The intensity of the AE should be defined based on the following three categories and according to medical and scientific judgment:

- Mild: Transient symptoms which are subjective or objective but no interference with the patient's daily activities. No change in dosage is needed to continue the treatment.
- Moderate: Marked symptoms with moderate interference with the patient's daily activities. Reduced dosage or unplanned treatment is necessary for the relief of adverse events.
- Severe: Considerable and unacceptable interference with the patient's daily activities. Discontinuation of the study drug is required because of significant adverse events.

To ensure that no confusion or misunderstanding of the difference between the terms 'serious' and 'severe' which are not synonymous, it should be noted that SAE does not necessarily correspond to serious or not serious AE to severe ones. All SAEs will be reported regardless of the intensity as mentioned above.

Causal relationship of adverse event

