3.2 Effectiveness Analysis Set

The subjects below shall be excluded from effectiveness analysis set in the following order:

- (1) Subjects who excluded from safety analysis set
- (2) Missing HbA1c value at both baseline and after administration of Trajent

4. Endpoints

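### SAP 3.1(6) does not say when dose and combination are judged, so changes after the first dose can take treated patients out of the main AE incidence and all effectiveness results

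*SAP*

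**What the plan says.** SAP 3.1 admits everyone who took Trajenta at least once. Citing a guideline of the Korean authority (MFDS), it then applies eight exclusions in order. The sixth is "6) Subjects who did not follow dosage/capacity". Its reference list is "The recommended dose 5 mg once daily", as monotherapy or combined with metformin, sulfonylurea, sulfonylurea plus metformin, insulin, insulin plus metformin, or empagliflozin 25 mg plus metformin. Nothing says whether the regimen is judged at the start, at any time, or over most of follow-up.

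The first exclusion from the effectiveness set in SAP 3.2 is "1) Subjects who excluded from safety analysis set", so every safety exclusion carries over.

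SAP 6.3.2 item 5, repeated in the table list of SAP 7.4, plans a separate AE tabulation that begins "For subjects excluded from the safety analysis set". It gives events by preferred term with incidence and 95% CI. Only never-treated patients and follow-up failures are left out of it.

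Protocol 7.3.1 states: "Safety analyses will be based on all patients treated, i.e. all patients who received at least one dose of Trajenta". It then provides for separate safety analyses where use went beyond the approved label. Protocol 3.3.2 requires "Patients who have been started on Trajenta in accordance with the approved label in Korea", which concerns the start of treatment.

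**The concern.** A rule with no time reference can be applied to what happens after the first dose, and the protocol foresees events that would trigger it. Its definition of moderate AE intensity includes the words "Reduced dosage or unplanned treatment is necessary for the relief of adverse events". A patient whose dose is reduced for that reason no longer matches the SAP's dose line. On background therapy, Protocol 4.2 says: "The protocol will allow additional drugs considered necessary for the patient's welfare to be prescribed at the discretion of the treating physician". If the added drug gives a combination outside the list, such as sulfonylurea plus insulin or any class not named, the patient no longer matches the combination line.

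Both kinds of change can follow from the outcomes under study. Safety is the primary objective, and the overall AE incidence (SAP 6.3), the comparisons by baseline characteristics and the logistic regression (SAP 6.3.1) all use the safety set. If patients leave that set because an AE changed their regimen, the denominator of the main safety estimate depends on the outcome. On the effectiveness side, no planned analysis brings these patients back into the HbA1c, FPG or responder results.

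**Working it through.** The plan states no figure on this point. The sample size of 3,000 is a regulatory requirement (Protocol 7.6) with no event rate, SD or power behind it, so there is nothing to reproduce. The check has a reading of the text and a sensitivity calculation.

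**1. What happens to a patient removed under (6)**

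| Result | Patient included? | Source |
|---|---|---|
| Overall AE incidence | No | SAP 6.3 |
| AE comparisons by baseline characteristics, logistic regression | No | SAP 6.3.1 |
| AE table for excluded patients | Yes, pooled with other exclusion reasons | SAP 6.3.2 item 5 |
| HbA1c, FPG, responders, final effectiveness assessment | No | SAP 3.2(1), 6.2 |

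The item 5 table also holds patients treated before the contract date, prescribed for another indication, in breach of eligibility, with a contraindication, or not Korean. It lists no breakdown by intensity, outcome or action taken. The triggering data are recorded: changes to Trajenta and to anti-hyperglycemic agents are collected at Visits 2 and 3 (Protocol 6.2.2.2 and 6.2.2.3).

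**2. AE incidence**

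Inputs: N = 3,000 from the protocol. The rest are assumptions: p = AE proportion in the retained set, e = share removed under (6), q = AE proportion among those removed.

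All-treated proportion = (1 − e)p + eq. The 95% CI half-width of the main-set estimate = 1.96 × √[p(1 − p) / (3,000(1 − e))].

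Worked case, p = 10%, e = 5%, q = 50%: 0.95 × 0.10 + 0.05 × 0.50 = 0.120. In counts, 285 of 2,850 retained plus 75 of 150 removed gives 360 of 3,000. Half-width = 1.96 × √(0.09 / 2,850) = 1.1 points.

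| e | All treated, q = 10% | q = 50% | q = 100% | Half-width (points) |
|---|---|---|---|---|
| 2% | 10.0% | 10.8% | 11.8% | 1.08 |
| 5% | 10.0% | 12.0% | 14.5% | 1.10 |
| 10% | 10.0% | 14.0% | 19.0% | 1.13 |
| 20% | 10.0% | 18.0% | 28.0% | 1.20 |

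With p = 20% and q = 50%, the all-treated figures are 20.6%, 21.5%, 23.0% and 26.0%, with half-widths of 1.45 to 1.60 points. At 2% removed and q = 50% the gap is inside the half-width for both values of p. At 5% it is 2.0 points against 1.10 for p = 10%, and 1.5 against 1.47 for p = 20%. The gap is zero whenever q = p.

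**3. HbA1c change**

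Let d = mean change in removed patients minus mean change in retained patients. Restoring the removed patients shifts the mean by e × d. For |d| = 0.5 percentage points and e = 2%, 5%, 10%, 20%, the shift is 0.010, 0.025, 0.050 and 0.100, against a standard error of about 0.02 if the SD is 1.0 (assumed). The sign of d is unknown. Poor control before the add-on makes d positive, and the glucose-lowering effect of the added drug makes it negative.

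**The case against.** The strongest reply is that the rule can be read as applying to the regimen at the start, in which case no outcome-driven removal occurs. The SAP does not exclude that reading. A reader might infer that (6) must apply at any time, because patients who began off-label already fall at step (5) for failing the inclusion criterion. That is suggestive but not conclusive. The contraindications in step (7) would also breach the label at the start, yet they are listed separately after (5), so the categories overlap and their order proves little.

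A reader might also infer that these patients' AEs disappear. They do not: item 5 reports them, and Protocol 7.3.1 itself foresees separate analyses for off-label use. What stands is that they cannot be told apart from other excluded patients and that no overall incidence includes them.

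Nor does every change trigger the rule. Adding metformin, sulfonylurea or insulin so as to reach a listed combination keeps the patient in. Moderate intensity can be met by unplanned treatment without a dose reduction, and stopping the drug is not named as a dose departure. Protocol 4.2 allows additional drugs in general terms, and 4.2.2.1 refers restrictions on them to the local label.

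Finally, the exclusions are said to follow an MFDS guideline that is not among the documents, and all analyses are descriptive. The sponsor may not be free to redefine the set. That limits the remedy to clarification and added analyses, but it does not supply the missing time reference.

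**Conclusion.** The point holds as an undefined rule that permits selection on events after the first dose. SAP 3.1(6) can take treated patients out of the main safety estimate that Protocol 7.3.1 bases on everyone with at least one dose, and SAP 3.2(1) takes them out of effectiveness altogether.

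The size cannot be determined from the documents, which give no AE, dose-change or add-on rates. If removed patients have more AEs than the rest, the main incidence is too low: 10.0% against 12.0% in all treated patients when 5% are removed and half of them had an AE. If the rates are equal, it is unaffected. A reader might infer that both the safety and the effectiveness results are tilted in the product's favour. The documents support this for safety only under that condition, and for HbA1c they do not support a direction at all.

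The remedy is cheap and protects the primary safety estimate, so it is worth making before the analysis is run.

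**What to change.** Keep the MFDS-based set and make four changes to the SAP:

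- **(a) 3.1(6):** state when dosage and combination are judged, preferably on the regimen at the start of Trajenta if the guideline permits.
- **(b) 6.3:** add an overall AE incidence with 95% CI in all treated patients, or at least in the safety set plus those excluded only under (6). Because exclusions are applied in order, a patient counted at (6) may also meet (7) or (8), so identify those who meet (6) alone.
- **(c) 6.2:** add a sensitivity analysis of HbA1c change, FPG change and the two responder rates that retains the same patients, with a note that it includes the effect of any added drugs.
- **(d) 6.3.2 item 5 and 7.4:** split the table by exclusion reason, so that patients removed under (6) can be seen on their own. This also serves the separate off-label analysis in Protocol 7.3.1.

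The cost is SAP wording and a few extra tables from data collected at Visits 2 and 3. The AE figure may turn out slightly less favourable. This concerns analysis sets only and implies no change to any dose or treatment.
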